The prior for the random center effects will be Normal centered at 0, and the hyperprior for the standard deviation of the random center effect will be specified in Section 6.5.3. Any baseline covariates that are added to the model (in sensitivity analyses to adjust for important unbalanced baseline covariates) will either be coded using 0/1 indicator variables, sets of indicator variables, or as centered continuous covariates. Priors for these other to-be-determined covariates are specified in Section 6.5.3. Post processing will be used to get posterior approximations of relative risk and risk differences due to treatment. The logistic model will be fit to the data, then for each infant, the model parameter chains will be used to estimate the within subject posterior relative risk and risk difference which will equal hypothermia divided by normothermia and hypothermia minus normothermia respectively. A within subject estimate of relative risk will be calculated by setting

the treatment variable value to hypothermia, estimating the probability of outcome for all infants, repeating the same process after setting the treatment variable to normothermia then dividing the two probabilities of outcome for all infants, hypothermia over normothermia. A within subject estimate of risk difference will be calculated by setting the treatment variable value to hypothermia, estimating the probability of outcome for all infants, repeating the same process after setting the treatment variable to normothermia then subtracting the two probabilities of outcome for all infants, hypothermia minus normothermia. Since the parameter chains will contain at least 120,000 samples, each infant will contribute at least 120,000 samples for the approximation of the within subject relative risk posterior and the within subject risk difference posterior. Using all samples of relative risk and risk differences from all infants to approximate the posteriors, the mean estimate of relative risk and risk difference will be calculated as well as, 95% credible intervals of mean relative risk and risk difference. Finally, posterior probabilities of benefit due to hypothermia from both relative risk and risk differences will be used as summary statistics. Differences in the relative risk and risk difference posteriors will be reflected upon to better understand the estimated treatment effect.

For count outcomes like days or duration, y_{ij} , the main covariates will have the form:

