6.5.5 Final Analysis

The final analysis will occur after 168 infants have completed the trial, as specified earlier. The final analysis will not occur until all enrolled infants have a primary outcome determination, i.e. have the primary endpoint value assigned, classified as withdrawn without primary outcome assigned, or deemed lost to follow-up. Part of determining primary outcome of enrolled infants will involve masked adjudication of outcomes for infants who have an indeterminable outcome based on partially collected follow-up information. Once all enrolled infants have reached final status and primary endpoints determined, the clinical database will be exported, and study analysis datasets created. At that point, the analysis datasets will be considered “locked” and any further adjustments to the clinical datasets will not be included in the analysis datasets.

The final analysis will involve posterior distribution estimation for the effect of hypothermia relative to normal cooling. For binary outcomes, the effect will be the adjusted relative risk and adjusted risk differences calculated from a binomial regression model with logit link and post processing of

predicted outcome probabilities. For count outcomes, the effect will be the adjusted relative risk from the two groups obtained using negative binomial regression. For ordinal outcomes, the effect will be the adjusted odds ratio calculated from the cumulative logits.

For treatment relative risk estimation, posterior probabilities of >0%, >5%, >10% and >20% decrease in binary outcomes will be calculated. If θ is the relative risk defined as risk in cooling group over risk in control group, then the above specified posterior probabilities are, $\Pr(\theta < 1 | X)$, $\Pr(\theta < 0.95 | X)$, $\Pr(\theta < 0.9 | X)$, $\Pr(\theta < 0.8 | X)$. In addition to posterior probability calculations, graphical displays of the posterior distribution and appropriate 95% credible intervals for the over-all relative risk will be created. Finally, forest plots of the center level relative risks and 95% credible intervals will be created.

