In addition to adjusting for level of encephalopathy and center in the logistic model, the final analysis of the primary outcome will also perform sensitivity analyses concerning possible treatment effect confounders present at randomization. These sensitivity analyses will adjust for baseline covariates that differ across the two treatments in addition to adjusting for level of encephalopathy and center. The additional covariates will be determined by comparing the primary outcome with respect to baseline characteristics listed in Section 5.3. More details about these sensitivity analyses are given in section 6.5.7. Secondary analyses may also adjust for covariates, but in such a case the analysis will only be completed with covariate adjustment. No secondary analyses will be completed twice, in the sense of one analysis without covariates and another analysis with covariates. These analyses will use the FAS population.

The lack of preexisting data suggests that the neutral prior distribution may be most appropriate for presentation of final results; however, generation of final results of the primary outcome analysis using the skeptical (RR of 1.10) and enthusiastic priors (RR of 0.75) will also be produced for the primary outcome to give a broad overview of the implications of the trial's efficacy results. Skeptical, neutral, and enthusiastic priors will also be utilized in the analysis of primary outcome components. All non-primary or non-primary component outcomes will be analyzed using only the neutral prior.

For treatment risk difference estimation, posterior probabilities of >0%, >1%, >2%, >3%, and >5% decrease in binary outcomes will be calculated (corresponding to NNTs of 100, 50, 33, and 20). If ψ is the risk difference defined as risk in normothermia group minus risk in cooling group, then the above specified posterior probabilities are, $\Pr(\psi < 0 | X)$, $\Pr(\psi < 0.01 | X)$, $\Pr(\psi < 0.02 | X)$, $\Pr(\psi < 0.03 | X)$, and $\Pr(\psi < 0.05 | X)$. In addition to posterior probability calculations, graphical displays of the posterior distribution and appropriate 95% credible intervals for the over-all risk difference will be created. Finally, forest plots of the center level risk differences and 95% credible intervals will be created.

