- Posterior plot of treatment effect
- Posterior median and posterior standard deviation
- 95% credible interval
- For relative risk, posterior probabilities of >0%, >5%, >10%, and >20% decrease in the primary outcome will be calculated
- For risk difference, posterior probabilities of >0%, >1%, >2%, >3%, and >5% decrease in primary outcome will be calculated
- forest plot of the center level effect and 95% credible intervals.

If the FAS analysis of the primary outcome results in any clinically notable findings, then the primary outcome may also be analyzed in an exploratory fashion using the PP population.

Analysis of Secondary Outcomes

With respect to secondary outcomes, analyses will follow the same process as the primary outcome analysis defined above. See MockTablesAppendix.docx for list of selected variables.

Analysis of Safety (AE) and Hospital Outcomes

Safety and hospital outcomes listed in Sections 6.2 and 6.3 will be analyzed using the FAS population and if necessary, the PP population using relative risk models, proportional odds models, or Negative Binomial models, depending on the type of outcome.

With respect to binary safety outcomes, the estimated posterior distribution of relative risk, θ , based on the data and the neutral prior will be used to determine posterior probabilities of harm from the intervention, $\Pr(\theta > 1 | X)$, as well as 95% credible intervals.

For ordinal safety outcomes, the estimated posterior distribution odds ratio for the cumulative logits, ϕ , will be estimated based on the data and the neutral prior. In addition, posterior probabilities of harm, $\Pr(\phi > 1 | X)$, and 95% credible intervals of ϕ will be calculated.

For count type safety outcome, the estimated posterior distribution of the treatment mean rate, ϕ , will be estimated based on the data and the neutral prior. In addition, posterior probabilities of harm, $\Pr(\phi > 1 | X)$, and 95% credible intervals of ϕ will be calculated.

Analysis of Ultrasound, CT scan, MRI and encephalopathy outcomes

Ultrasound, CT scan, MRI, and encephalopathy outcomes will be analyzed using the FAS population. Head ultrasounds, CT scans, and brain MRIs will be summarized by treatment and time (prior to intervention, during intervention, after intervention, any time). Summaries will be created for number of babies with any abnormal findings during time period data recorded, and for total events across all babies during any time period.

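### The formulas for the risk-difference probabilities of benefit in SAP 6.5.5 point the wrong way: as written they give the probability of no such benefit

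*SAP*

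**What the plan says.** Section 6.5.5 (Final Analysis) sets the target in words: "posterior probabilities of >0%, >1%, >2%, >3%, and >5% decrease in binary outcomes will be calculated". It ties the non-zero thresholds to numbers needed to treat, "corresponding to NNTs of 100, 50, 33, and 20". The risk difference ψ is then "defined as risk in normothermia group minus risk in cooling group, then the above specified posterior probabilities are, $\Pr(\psi < 0 | X", and so on: the five probabilities are written as Pr(ψ < 0), Pr(ψ < 0.01), Pr(ψ < 0.02), Pr(ψ < 0.03) and Pr(ψ < 0.05), each given the data.

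The list of results for each primary-outcome analysis, later in 6.5.5, repeats the target without formulas: "For risk difference, posterior probabilities of >0%, >1%, >2%, >3%, and >5% decrease in primary outcome will be calculated".

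Section 6.5.1 (Statistical Methods), which describes the post-processing of the logistic model, takes the difference in the other order: "then subtracting the two probabilities of outcome for all infants, hypothermia minus normothermia".

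For comparison, the relative risk θ in 6.5.5 is the "relative risk defined as risk in cooling group over risk in control group", with the probability of any decrease written as Pr(θ < 1). That definition and that inequality agree with each other.

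**The concern.** The modelled event is the bad outcome (death or moderate/severe disability is coded 1 in 6.5.1), so benefit means a lower risk under cooling. If ψ is normothermia minus cooling, benefit is positive ψ, yet the formulas collect the posterior mass below each threshold. Two sections also give the risk difference opposite signs, so a programmer has to choose between them, and the formulas are not fully right under either.

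Risk difference accounts for three of the six planned analyses of the primary outcome (enthusiastic, neutral and skeptical prior), and 6.5.5 says that secondary outcomes follow the same process. Section 6.5.1 names the posterior probabilities of benefit on both scales as summary statistics and intends to interpret differences between the two posteriors. A sign error would create such a difference where none exists.

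**Working it through.** **Inputs.** Thresholds x = 0, 0.01, 0.02, 0.03, 0.05, the definition of ψ and the written inequalities: SAP 6.5.5. Opposite definition, RD = hypothermia − normothermia: SAP 6.5.1. Relative risk θ = cooling/control: SAP 6.5.5.

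**1. What the thresholds mean.** NNT = 1/x gives 1/0.01 = 100, 1/0.02 = 50, 1/0.03 = 33.3 and 1/0.05 = 20. These reproduce the stated NNTs, so the thresholds are absolute risk reductions. The zero threshold has no finite NNT, which is why five thresholds go with four NNTs.

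**2. Sign as in 6.5.5.** A decrease of more than x means risk(normothermia) − risk(cooling) > x, that is ψ > x. The target is therefore Pr(ψ > x) = 1 − Pr(ψ ≤ x). The SAP writes Pr(ψ < x), the complement, at all five thresholds.

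**3. Sign as in 6.5.1.** With RD = −ψ, a decrease of more than x is RD < −x. Putting RD into the written formulas gives Pr(RD < +x). This is right at x = 0 only; at the other four thresholds it counts harms of up to x as benefit.

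**4. Check against the relative risk.** Both effects come from the same two predicted probabilities for each infant and each draw. Hence θ < 1 exactly when ψ > 0, and Pr(θ < 1) and Pr(ψ < 0) add up to 1 (apart from exact ties). Section 6.5.5 offers both as the probability of a decrease above 0%.

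**5. Check by nesting.** A decrease above 5 points is also a decrease above 1 point, so the probability must fall as x grows. The written expressions rise with x under either sign.

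**6. Size, with assumed normal posteriors.** For ψ ~ N(m, s): correct value 1 − Φ((x − m)/s); as written with the 6.5.5 sign Φ((x − m)/s); as written with the 6.5.1 sign Φ((x + m)/s).

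| Assumed m, s | x | Correct | Written, 6.5.5 sign | Written, 6.5.1 sign |
|---|---|---|---|---|
| 0.10, 0.075 | 0 | Φ(1.33) = 0.91 | 0.09 | 0.91 |
| 0.10, 0.075 | 0.05 | Φ(0.67) = 0.75 | 0.25 | Φ(2.00) = 0.98 |
| 0, 0.07 | 0.05 | 1 − Φ(0.71) = 0.24 | 0.76 | 0.76 |

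**7. Size, with the SAP's priors.** This is a grid posterior for a two-arm logistic model with intercept N(0, 1) and neutral log odds ratio N(0, 0.7072) from 6.5.3, leaving out the encephalopathy and center terms. Assumed data: 84 infants per arm (168/2), with 59/84 events under normothermia and 42/84 under cooling, close to the 70% versus 50% scenario in section 3.4. Pr(θ < 1) is 0.991.

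| x | Correct | Written, 6.5.5 sign | Written, 6.5.1 sign |
|---|---|---|---|
| 0 | 0.991 | 0.008 | 0.991 |
| 0.01 | 0.987 | 0.013 | 0.994 |
| 0.02 | 0.981 | 0.019 | 0.996 |
| 0.03 | 0.974 | 0.027 | 0.998 |
| 0.05 | 0.950 | 0.050 | 0.999 |

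(At x = 0, 0.991 and 0.008 fall just short of 1 because some grid points lie exactly at no difference.) With the arms exchanged, so that cooling is clearly harmful, the written formulas with the 6.5.5 sign give 0.993 to 0.999 as the probability of a decrease; the correct values are 0.006 or less.

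**The case against.** The strongest reply is that nobody would be misled. The target is stated in words twice, the NNTs confirm it, the relative-risk formulas beside it are correct, and the operative list of results does not use ψ. Literal coding would also show itself: in the first normal example above, 0.91 on the relative-risk scale would stand next to 0.09 on the risk-difference scale, and the posterior median, interval and plot required for each analysis show the direction. The only design criterion stated in the SAP (section 3.4) is a posterior probability of at least 0.80 for RR < 1, and no decision rule rests on ψ. Minus signs might also have been lost when the PDF was read.

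Most of this stands as a limit on the consequence. The intent can be recovered, the harm arises only if the formulas are programmed as written, and the relative-risk results and risk-difference estimates are unaffected. It does not make the formulas right. The cross-check is also weakest where it is most needed: a programmer who takes the difference from 6.5.1 and the thresholds from 6.5.5 gets a zero-threshold value that agrees with the relative risk, while the other four values are too high, in favour of cooling. Lost minus signs would not help either, because Pr(ψ < −x) with ψ as worded in 6.5.5 is the probability of a harm larger than x.

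**Conclusion.** The formulas are wrong as written. Under the definition in the same sentence, all five are complements of the stated quantity; under the definition in 6.5.1, four of the five are wrong. This follows from the SAP's definitions alone and needs no assumption.

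The numerical size does rest on assumptions (the normal posteriors, and the event counts and reduced model in the grid example). In those examples a true probability of 0.75 for a decrease above 5 points becomes 0.25 or 0.98 depending on the sign used, and with no effect 0.24 becomes 0.76. Because these are pre-specified quantities for the primary outcome, they should be corrected and not left to the programmer's interpretation.

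**What to change.** Use one sign in 6.5.1 and 6.5.5, and match the inequalities to it. Either of these is correct:

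- ψ = normothermia − cooling, reporting Pr(ψ > 0), Pr(ψ > 0.01), Pr(ψ > 0.02), Pr(ψ > 0.03) and Pr(ψ > 0.05), with 6.5.1 changed to the same order; or
- RD = hypothermia − normothermia as in 6.5.1, reporting Pr(RD < 0), Pr(RD < −0.01), Pr(RD < −0.02), Pr(RD < −0.03) and Pr(RD < −0.05), with the definition in 6.5.5 changed.

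Reversing the definition of ψ alone is not enough, since it repairs only the zero threshold. The code should be checked for two properties: the zero-threshold probability equals Pr(θ < 1), and the probabilities do not rise with the threshold. The cost is a sentence in the SAP and a line of post-processing; no model needs refitting and there is no downside.

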3.7 Timing of Interim and Final Analysis

Final analyses were planned to occur after 168 infants were consented, enrolled, randomized, and followed to 18-22 months corrected age. The study analysis database is constructed using those who died before the 18-22 month follow-up and all survivors not lost to follow-up who underwent protocol-specified neurodevelopmental assessment.

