4.3 Analysis Datasets

This analysis will use two analysis populations, a full analysis set (FAS) and per-protocol (PP).² The FAS analysis population will include all randomized infants with ascertained primary outcomes. This FAS analysis population is recognized as being as close as possible to an intent-to-treat population. All analyses based on the FAS will analyze infants as randomized. The PP analysis population will include all infants who received their randomized treatment (72 hours of hypothermia or normothermia) and have a determined primary outcome. All analyses based on the PP will analyze infants as treated.

² ICH E9: <https://www.fda.gov/regulatory-information/search-fda-guidance-documents/e9-statistical-principles-clinical-trials>

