5.2 Withdrawal / Follow-up

- Infants can be lost-to-follow-up between Network Status (120 days after birth, or time of discharge/transfer) and the time of the scheduled 18-22-month follow-up visit (although the Covid pandemic did require some subjects to undergo follow-up at later dates). The Premie Hypothermia PH13 form is completed at the time of network status. Infants cannot be lost prior to network status.
- Infants who withdraw from the study will not have any data collected beyond the timepoint of withdrawal. Data collected prior to withdrawal will be available for summarization and analysis.
- Numbers of infants who withdraw or are lost to follow-up will be presented in the CONSORT diagram.

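### Short-term safety, hospital-course and imaging outcomes are analysed only in infants whose 18-22 month outcome is known, so early data already collected are left out

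*SAP*

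**What the plan says.** Section 2.2 makes short-term safety, within 108 hours of baseline, the second primary objective.

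For the final analysis, Section 6.5.5 says "Safety and hospital outcomes listed in Sections 6.2 and 6.3 will be analyzed using the FAS population" and, if necessary, in the per-protocol set. For imaging it says "CT scan, MRI, and encephalopathy outcomes will be analyzed using the FAS population".

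Section 4.3 defines only these two populations. "The FAS analysis population will include all randomized infants with ascertained primary outcomes". The per-protocol definition ends with the words "72 hours of hypothermia or normothermia) and have a determined primary outcome". Section 3.7 builds the database on the same lines: "The study analysis database is constructed using those who died before the 18-22 month follow-up and all survivors not lost to follow-up".

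Section 5.2 describes what exists for the other infants. "Infants cannot be lost prior to network status", where network status is 120 days, or discharge or transfer. For infants who withdraw, "Data collected prior to withdrawal will be available for summarization and analysis". Section 6.5.5 expects some infants to finish the trial "classified as withdrawn without primary outcome assigned, or deemed lost to follow-up".

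**The concern.** Membership of both analysis sets depends on something learned about 18-22 months after the safety window has closed. An infant with a complete 108-hour record and a complete hospital record who is lost at one year belongs to neither set. The plan thus calls the early data available in one section and assigns the analysis to sets that exclude them in another.

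Three things are at stake:

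- **Information on rare serious adverse events** is discarded in a trial that Section 3.4 says was not powered in the traditional sense.
- **The rate of death before discharge** (Section 6.3) is distorted. A known death is itself an ascertained primary outcome, so every known in-hospital death stays in the FAS. Infants alive at network status and lost later leave the denominator.
- **Denominators may not agree.** The descriptive summaries in Section 6.5.1 use non-missing values and name no analysis set, so they can have a different denominator from the modelled results.

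**Working it through.** **Tracing one infant.** Take an infant who is randomised, treated, discharged alive and then lost.

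| Section | Consequence |
|---|---|
| 5.2 | Loss happened after network status, so the 108-hour and hospital data exist |
| 6.5.5 | Final status is lost to follow-up, with no primary outcome |
| 4.3 | In neither the FAS nor the per-protocol set |
| 3.7 | Not in the analysis database |
| 6.5.5 | Not in the safety, hospital-course or imaging models |

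Masked adjudication (Section 6.5.5) covers infants with partly collected follow-up information. It makes the excluded group smaller but does not restore infants with no determinable outcome.

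**Size.** The planned number is 168 (Section 3.4). The SAP gives no loss rate, death count or adverse event count, so all of these are assumptions below. Let n be the number left in the FAS.

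| Assumed share without outcome | 5% | 10% | 15% |
|---|---|---|---|
| Infants excluded (168 × share, rounded) | 8 | 17 | 25 |
| n | 160 | 151 | 143 |
| Standard error factor, √(168/n) | 1.025 | 1.055 | 1.084 |
| Maximum factor on death rate, 168/n | 1.05 | 1.11 | 1.18 |
| Death before discharge, 20 known deaths (20/168 = 11.9%) | 12.5% | 13.2% | 14.0% |
| Chance that at least one of 2 rare events is left out, 1 − C(n,2)/C(168,2) | 9% | 19% | 28% |

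The death factor is a maximum because it takes every excluded infant to have been alive at discharge. An infant who withdrew before network status might have died unrecorded. With d such deaths the true rate is (20 + d)/168. Setting this equal to 20/n gives d = 20 × (168/n − 1) = 1.0, 2.25 and 3.50. The overstatement is therefore gone once 1, 3 or 4 such deaths occurred.

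**Comparison between arms.** Assume 84 infants and 10 deaths per arm.

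- Equal loss: relative risk 1.00, unchanged.
- 8% loss under hypothermia and 12% under normothermia: 7 and 10 infants leave, so (10/77)/(10/74) = 74/77 = 0.96. With the losses reversed it is 1.04. On a normal approximation to the log odds ratio with the neutral prior Normal(0, 0.7072), without center or encephalopathy terms, Pr(harm) is 0.47 or 0.53 instead of 0.50.
- A wider gap, 5% versus 15%: 4 and 13 infants leave, and with equal deaths the relative risk is 80/71 = 1.13 when the larger loss is under hypothermia.

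**Non-fatal events.** The direction depends on who is lost.

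- If exclusion is unrelated to the event, the expected rate does not change. With 24 events in 168 (14.3%) and 17 infants excluded at random, 0 to 5 events are lost in the central 95% of cases. The observed rate then runs from 19/151 = 12.6% to 24/151 = 15.9%.
- If the event is tied to death, the rate rises. Take 21 deaths per arm of 84 (25%), the event in 60% of deaths and 20% of survivors, and 13 survivors lost. The true rate is (12.6 + 12.6)/84 = 30.0%, and the FAS rate is (12.6 + 10.0)/71 = 31.8%.

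**Separate error in Section 6.2.** The safety variable for spontaneous intestinal perforation requires the event date to equal the birth date. A perforation on a later day within the 108-hour window of Section 2.2 would not be counted. That entry also cites item G.5 of form PH15, whereas Section 6.3 takes item G.5 from form PH13.

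**The case against.** The best defence is that little changes where it matters. Safety inference in Section 6.5.5 is a comparison between arms, and under equal loss the death relative risk stays at 1.00. The one bias with a clear direction concerns death before discharge, a hospital-course outcome, not the general run of 108-hour events. All sizes rest on assumed rates. This stands, and it limits the weight of the point.

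It can also be said that interim safety analyses were done under the protocol, that further imaging analyses have their own SAP, and that the mock tables, which are not at hand, may show other denominators. None of these changes the set that Section 6.5.5 fixes for the final models. The description of the FAS in Section 4.3 as close to intention-to-treat supports its use for the 18-22 month outcome. It gives no reason to condition a 108-hour outcome on that visit.

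A fair practical objection is that all randomised infants is not a complete recipe. Baseline is insertion of the esophageal probe, and Section 4.2 foresees infants in whom the intervention never started or consent was absent. Coding an infant who withdraws during the window as event-free would understate risk. These cases need a written rule, but they do not justify dropping infants whose window is complete.

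On the perforation item, Section 6.3 counts perforations without a date limit, so later ones still appear under hospital course. Only the safety-window row is affected.

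**Conclusion.** The concern holds. As written, the plan models a primary objective in a subset defined by much later follow-up and leaves out early data that it calls available. The definitions alone establish this. The size depends on the unstated loss rate: for 5 to 15% without an outcome, 8 to 25 of 168 infants are excluded, standard errors widen by 2.5 to 8.4%, and the in-hospital death rate is multiplied by up to 1.05 to 1.18. That upper bound assumes the excluded infants were alive at discharge.

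The direction for non-fatal events cannot be known from the document. The arm comparison is little affected unless loss differs by arm, which the document does not show. The primary efficacy analysis is untouched. This should be corrected because the loss of information is avoidable and the remedy costs almost nothing.

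**What to change.** 1. In Section 4.3, add a population of all randomised infants, analysed as randomised, with data up to withdrawal. In Section 6.5.5, assign to it the outcomes of Sections 6.2 and 6.3, including death before discharge, and the imaging outcomes. Keep the FAS for outcomes that need the 18-22 month visit.
2. State how infants with no baseline time, and infants withdrawn during a window without an event, enter the denominators. Report per arm how many withdrew before each window ended.
3. Bring Section 3.7 into line so that the database holds all randomised infants, and name the set used for the descriptive summaries in Section 6.5.1.
4. As a separate correction, define the safety perforation outcome in Section 6.2 by an event date from baseline to 108 hours after baseline, and reconcile the form reference (PH15 or PH13, item G.5) with Section 6.3.

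The cost is SAP wording, one added population and new denominators in the safety, hospital and imaging tables. No new data are needed. The only drawback is that numbers of infants will differ between the safety and efficacy tables, which a footnote can explain.
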